### 9.3.2 Discontinuation Criteria Related to the Study Site

Discontinuation of the clinical study in an individual study site may occur because of various reasons including but not limited to:

- Failure of Investigator to comply with the ICH-GCP and/or applicable regulatory requirements. This includes failure to adherence to data protection and data security requirements if occurring repeatedly.
- Submission of knowingly false or incomplete information from the site to the Sponsor, study monitor, or the authorities.
- Repeated non-adherence to protocol requirements including insufficient data quality (missing data in (e)CRFs occurring repeatedly).
- Failure of the Investigator at a site to enrol patients into the study/ Excessively slow recruitment.
- Lack of study activity (i.e. all patients have completed the study and all obligations have been fulfilled).

### 9.3.3 Discontinuation Criteria Related to the Patient

The patients will be advised in the Informed Consent Forms that they have the right to withdraw from the study at any time without prejudice and may be withdrawn at the Investigator's / Sponsor's discretion at any time.

Withdrawal of individual patients from treatment or from the study respectively is caused by (but is not limited to) the following reasons:

- Pregnancy detected at any time during the study.
- At the discretion of the Investigator
- Disease progression requiring the use of effective MS treatment (DMT)
- Major protocol deviation(s)
- Ineligibility/Development of one or multiple protocol-specified withdrawal criteria
- Adverse Event
- At the specific request of the sponsor
- The patient withdraws of consent
- Lost to follow-up

In case a patient does not reappear to any scheduled visit (i.e. is lost to follow-up) reasonable effort should be made to contact this patient in order to complete assessments and/or to evaluate the reason for non-appearance (possibly implicit withdrawal of consent). These contact attempts

should be documented in the medical records. Should the patient continue to be unreachable, he/she will be considered to have withdrawn from the study with a primary reason of lost to follow-up.

In the event that a patient withdraws consent or is withdrawn from the study, the study termination page in the (e)CRF should be completed indicating that the study was prematurely terminated. The Investigator should record the date of the withdrawal and the reason for withdrawal.

If a subject wishes to withdraw his/her consent to the testing of his/her samples, the Investigator must inform the Sponsor in writing of the subject's wishes and enter the date of withdrawal in the subject's electronic Case Report Form (eCRF).

Patients who received at least one dose of CLS12311 and prematurely discontinue the treatment phase stay in the study and follow the schedule of assessments in the treatment phase. If a patient withdraws from the study, the patient should be encouraged to return for the ED visit (see section 14.1.9) and asked if he or she can still be contacted for further information. The outcome of that discussion should be documented in both the medical records and in the eCRF.

Female patients with a suspected unplanned pregnancy during the study must permanently discontinue the study, contact their study investigator to confirm the pregnancy by urine pregnancy testing.

## 10 STUDY TREATMENT

Investigational Medicinal Product (IMP) and placebo will be made available to the study sites by TETEC AG, Reutlingen, Germany on behalf of Cellerys AG, Zurich, Switzerland (Sponsor of the study). If defects in the IMP or placebo are observed, the study manager or the monitor is to be informed.

### 10.1 Name and Description of the Investigational Medicinal Product and Placebo

#### 10.1.1 Qualitative and Quantitative Composition

The IMP, CLS12311, consists of autologous red blood cells (RBCs) that have been chemically coupled with [REDACTED] peptides [REDACTED]

[REDACTED] from [REDACTED] proteins [REDACTED]

[REDACTED] expressed in the brain and re-suspended in saline (150 ml). [REDACTED]

[REDACTED]

[REDACTED]

[REDACTED]

The placebo consists of (uncoupled) autologous red blood cells (RBCs) re-suspended in saline (150 ml).

A detailed description of the IMP and placebo is available in the Investigator Brochure.

RBCs for CLS12311 and placebo will be isolated from 450 - 500 ml of whole blood collected of study qualifying MS patients taken by standard blood donation procedures. The blood bag containing RBCs will be transferred to TETEC AG, Reutlingen, Germany, where CLS12311/placebo will be manufactured in compliance with Good Manufacturing Practice (GMP). A complete Certificate of Analysis (CoA) is available for each batch, including batch numbers, storage conditions, and expiry dates, ensuring full traceability.

Transport and handling protocols have been established to maintain the integrity of RBCs, CLS12311, and placebo samples during the transfer to and from TETEC AG.

Informed consent is obtained from all patients before blood collection, specifically addressing both the main study and the research use of the buffy coat. The consent form outlines that the buffy coat will be sent to Cellerys AG for exploratory research use.

Table 10-1 presents the composition of the Investigational Medicinal Product (IMP) and placebo.

**Table 10-1 Composition of drug product (CLS12311) and placebo**

Ingredient	Investigational medicinal test product CLS12311	Placebo
Autologous peptide-coupled RBCs	■■■■ cells (range ■■■■ ■■■■ ■■■■ ■■■■)	-
Autologous RBCs (uncoupled)	-	■■■■ cells (■■■■ ■■■■ ■■■■ ■■■■)
Saline (NaCl 0.9%)	Filled up to the total volume of 150 ml (135 – 165 ml)	Filled up to the total volume of 150 ml (135 – 165 ml)

### 10.1.2 Pharmaceutical Form

CLS12311 and placebo are supplied as a sterile and preservative-free solution for i.v. infusion.

### 10.1.3 Nature and Content of Container(s)

CLS12311 and placebo are packaged in a 500 ml standard bag (CompoFlex, Fresenius Germany). The sterile bag is made of PVC/DHEP (Polyvinyl chloride).

CLS12311 drug product/placebo is supplied for single-use only.

## 10.2 Posology and Method of Administration

### 10.2.1 Dosage

[figure not shown]
Ascending doses of CLS12311 will be given as follows:

- **Group 1**
  - 2 patients (patient 1 and 2): ■■■■ peptide-coupled RBCs followed by a single bag placebo at ■■■■ and two bags of placebo at ■■■■ (from a single blood donation), corresponding to a total dose of ■■■■ peptide-coupled RBCs.
  - 1 patient (patient 2) will receive a second treatment of ■■■■ peptide-coupled RBCs followed by a single bag placebo at ■■■■ and two bags of placebo ■■■■ (from a single blood donation), corresponding to a cumulative total dose of ■■■■ peptide-coupled RBCs in the trial.
- **Group 2**
  - 3 patients (patients 3, 4 and 5): ■■■■ peptide-coupled RBCs followed by a single bag placebo ■■■■ (from a single blood donation), corresponding to a total dose of ■■■■ peptide-coupled RBCs.
  - 2 patients (patients 4 and 5): will receive a second treatment of ■■■■ peptide-coupled RBCs followed by a single bag placebo ■■■■ (from a single blood donation), corresponding to a cumulative total dose of ■■■■ peptide-coupled RBCs in the trial.
- **Group 3**
  - 4 patients (patients 6-9): ■■■■ peptide-coupled RBCs (i.e. ■■■■ ■■■■ peptide-coupled RBCs) ■■■■ (from a single blood donation), corresponding to a total dose of ■■■■ peptide-coupled RBCs.

- 3 patients (patients 7-9): [REDACTED] peptide-coupled RBCs (i.e. [REDACTED] [REDACTED] peptide-coupled RBCs) [REDACTED] (from a single blood donation, corresponding to a cumulative total dose of [REDACTED] peptide-coupled RBCs in the trial.

A dose of [REDACTED] peptide-coupled RBCs is equivalent to one blood bag.

Dosing is outlined in Figure 10-1.

### 10.2.2 Statement on the use of uncoupled RBCs “placebo”

To reach the [REDACTED] peptide-coupled RBCs for the high-dose group (group 3), two blood bags per dose are required. For this reason, it is aimed that two blood bags per dose are also administered in the low and medium dose groups (groups 1 and 2) to ensure that the cell count administered is equivalent in all patients. Thus, patients in the low and medium dose groups receive a reinfusion of uncoupled RBCs ("placebo").

Administration of uncoupled RBCs is considered important for the evaluation of safety and tolerability of CLS12311, as the re-infusion of RBCs can counteract the risks of iron deficiency and/or anaemia induced by the blood donation. This is particularly relevant for the second treatment cycle, as differences respective lab values would be expected across the dose groups, if the cell number would not be standardized between the treatment arms. In addition, administering uncoupled cells will maintain dose blinding for both patients and investigators and hence provide an unbiased evaluation of CLS12311's safety and efficacy. The use of autologous uncoupled RBCs will not expose patients to any risk of serious or irreversible harm, ensuring compliance with regulatory requirements for minimizing participant risk while maintaining study integrity.

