### 3 PROTOCOL SUMMARY / SYNOPSIS

Study title	Multicenter, Phase Ib/Ila Study on the Safety and Efficacy of Autologous Peptide-coupled Red Blood Cells in Patients with Relapsing Remitting Multiple Sclerosis
Brief study title	Peptide-coupled Red Blood Cells for the Treatment of Multiple Sclerosis
Acronym	RED4MS
Version Number	7.0
Version Date	2025-05-09
Development phase	Phase Ib
Study No.	MSB-IG-H-2101
EU-CT No.	2023-510127-30-00
Study drug	Peptide-coupled red blood cells (CLS12311)
Coordinating Investigator	
████████████████████
 
████████████████████
 
██
 
████████████████████
 
████████████████████████████
 
████████████████████████████████

Sponsor	Cellerys AG [name]  EU legal representative: SCOPE International [name]
CRO	SCOPE International [name] [contact] E-Mail: [contact]
Study design	Phase Ib open-label trial evaluating ascending-doses of CLS12311  Note: Originally, the study was designed to include a Phase IIa part (Part B). The Phase IIa (Part B) will not be conducted. This amendment reflects the adjustment to a Phase Ib only design.
Study objectives	Safety Objective Primary safety objective: 

To assess the safety and tolerability of CLS12311 in patients with relapsing remitting multiple sclerosis (RRMS)

 Secondary safety objective: 

To assess the safety and tolerability of each dose group of CLS12311

 Exploratory objective 

To understand the mechanism/s of action of tolerance induction with peptide-coupled RBCs and to identify biomarkers for measuring immune tolerance induction

Primary endpoint	Safety endpoint 
 
Safety and tolerability of CLS12311 measured by the number and severity of treatment-emergent adverse events (TEAEs) and treatment emergent serious adverse events (TESAEs) and/or worsening of disease by clinical (relapses) and imaging (number and size of brain MRI lesions)
 
 
MRIs will be assessed centrally by independent readers.

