## 7 STUDY DESIGN

Open-label, ascending-dose Phase Ib trial to evaluate the safety and tolerability of three doses of CLS12311 in patients with relapsing-remitting multiple sclerosis (RRMS).

The study will be conducted at approximately 12 sites in Europe.

The total duration will be at least 48 weeks for each participant and will include a total of 16 visits divided into two phases: an open-label treatment phase and a safety follow-up phase. The study phases are described in more detail in the following paragraphs.

Patient eligibility will be assessed during the Visit 1 (week 0) at baseline, where general patient and disease characteristics will be recorded. Patients who meet the criteria for enrollment will be sequentially allocated to one of the dose groups. The allocation to the dose group and the timing of treatment administration will be centrally coordinated to ensure appropriate safety assessments between dosing of patients. Hence, the time-period between [REDACTED] might vary between patients.

If safety and tolerability during the first treatment cycle, a subset of patients will receive a second administration of CLS12311 in a dose escalating second treatment cycle. Additional information on the rationale of the study design is given in section 5.2.3.

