#### 19.1.4 Steering Committee

A Steering Committee consisting of at least the Sponsor and selected country Investigators, or other experts will be established to provide oversight of the conduct of the trial. This includes oversight of the practical aspects of the study as well as ensuring that the study is conducted in a way which is both safe for the patients and provides appropriate safety and efficacy data to the Sponsor and Investigators.

Specific responsibilities of the Steering Committee may include, but are not limited to, the following:

- to provide overall supervision of the trial, including compliance with regulatory standards
- to discuss steps to reduce deviations from the protocol
- periodic review of the study progress
- to review safety data; in a blinded manner. This review is typically done blinded to treatment allocation

- to resolve any differences within the research team or between research team and Sponsor regarding data management and monitoring procedures in the trial or any recommendation for modifications to the protocol.
- The Steering Committee provides guidance to the Sponsor regarding modifications of the trial conduct based on DSMB recommendations, e.g. prematurely stopping recruitment and/or treatment, reducing the dose for a specific dose group or terminating the clinical trial.

Details regarding composition of the Steering Committee, its premise and scope will be specified in the Steering Committee charter. Members will agree their commitment to the charter in writing prior to the start of the study.

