2.4 Randomization

Randomization is not applicable for this study.

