2.7 Blinding

Participants of the study will remain unblinded with regard to the dosing regimen.

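### Protocol 10.2.2 claims dose blinding and an unbiased evaluation, which this open-label trial does not provide

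*Protocol*

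**What the plan says.** Protocol 10.2.2 gives two kinds of reason for infusing uncoupled cells in the low and medium dose groups. The first is physiological: an equal cell count in all patients, and an offset to anaemia or iron deficiency caused by the blood donation. The second concerns bias: "administering uncoupled cells will maintain dose blinding for both patients and investigators and hence provide an unbiased evaluation" of the product's safety and efficacy.

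Elsewhere the design is described differently. The synopsis calls it an "open-label trial evaluating ascending-doses of CLS12311", and Protocol 7 an "Open-label, ascending-dose Phase Ib trial to evaluate the safety and tolerability of three doses of CLS12311". SAP 2.3 agrees with both. SAP 2.4 says "Randomization is not applicable for this study", and SAP 2.7 says "Participants of the study will remain unblinded with regard to the dosing regimen". Protocol 7.2 also describes the safety follow-up as unblinded.

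Protocol 19.1.4 contains one other blinding statement, on the Steering Committee's review of safety data: "This review is typically done blinded to treatment allocation".

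**The concern.** A protocol that says its assessments are protected by dose blinding invites the report to say the same. Here the main outcomes depend on clinical judgement. Site investigators grade adverse-event severity (Protocol 13.1.3) and assign causality (13.1.4). The investigator or a study physician scores the EDSS (12.2.1.4). The investigator makes the initial relapse report (12.1.1.2). The secondary objective is safety and tolerability in each dose group, so these judgements are tabulated by dose.

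They also have consequences during the trial. An adverse event of special interest must be both severe and related to the product (Protocol 12.1.1.1, SAP 5.5.1). Two of the four events that require a DSMB meeting are defined by severity together with relatedness within a dose level. If the assessor can work out the dose, expectation can enter these judgements, and 10.2.2 tells the reader that it cannot.

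**Working it through.** The plan gives no figure to reproduce. The check sets the blinding claim against the design and asks whether anything in the text could conceal the dose.

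1. **Design label.** The synopsis, Protocol 7, the heading of Protocol 7.1 and SAP 2.3 all say open-label. That word alone could coexist with a masked dose level, but SAP 2.7 closes the gap for participants by naming the dosing regimen.

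2. **Allocation.** "Patients who meet the criteria for enrollment will be sequentially allocated to one of the dose groups" (Protocol 7). Protocol 10.2.1 and SAP 2.5.1 print the map: patients 1 and 2 receive the low dose, patients 3 to 5 the medium dose and patients 6 to 9 the high dose. That is 2 + 3 + 4 = 9 positions, each with exactly one dose. Anyone holding the protocol who knows a patient's place in the sequence knows the dose, whatever the bags look like.

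3. **What the bags do.** From the dosing scheme in the synopsis, each cycle has two treatment days with two bags, so four bags in every group. Coupled bags number 1 of 4 (low), 1 + 1 = 2 of 4 (medium) and 2 + 2 = 4 of 4 (high). The uncoupled bags bring every group to four. That equalizes volume and cell count. It would be necessary for masking but is not sufficient.

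4. **Masking procedure.** The visible text describes no concealment of bag contents, no code-break procedure and no site assessor kept unaware of dose. Some provisions point the other way. A footnote to the schedule of events says that dose group 1 gets only placebo at one visit, and Protocol 12.1.1.1 describes the recorded relationship by product, distinguishing CLS12311 from placebo.

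5. **From blinding to lack of bias.** Even perfect masking would not make contrasts between dose groups unbiased, because the groups are filled in calendar order without randomization. So the inference in 10.2.2 fails at its second step as well as its first.

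6. **Which outcomes are exposed.** Adverse-event causality and severity, EDSS and the investigator's relapse report are judged at the site. MRI is read centrally by independent readers, and an expert neurologist reviews relapses. Neither is stated to be unaware of dose group, nor is either stated to know it.

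7. **DSMB triggers (synopsis).** The four are: a severe adverse event at least possibly related; moderate, at least possibly related events in three patients; a lesion-count increase in three patients; and a confirmed severe relapse soon after dosing. The first two rest on the site's severity and relatedness judgements.

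**The case against.** The best defence is that this is one supporting sentence in a rationale section. The main reason for the uncoupled bags is physiological and stands. No planned output depends on blinding, every analysis is descriptive, and the SAP already says the trial is open-label, non-randomized and unblinded. All of that is correct. It limits the consequence but does not remove the contradiction. SAP 7 reports no departure from the protocol, and Protocol 20 bases the study report on the protocol, so nothing in the plan flags the sentence as wrong. It may be left over from the dropped Part B, but the documents do not say so.

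Several stronger readings are tempting and are not supported:

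- *Every judgement was made with the dose known.* In SAP 2.7, participants may mean patients only. The 1-to-9 order runs across the trial, whereas patient IDs are built from country, site and serial number (Protocol 9.2), and allocation is central across about 12 sites. For investigators the text supports knowable, not known.
- *The trial compares dose groups and the comparison is biased.* The secondary objective is to assess each dose group. No comparison or hypothesis is planned.
- *One re-judged event shifts incidence by 50, 33 or 25 percentage points.* These are 1/2, 1/3 and 1/4: what any single patient contributes in groups of 2, 3 and 4, blinded or not. They do not measure bias. The denominators may also be larger, since the safety set counts all blood donors and some patients who discontinue are replaced.
- *The central readers received the dose group.* No visible text says what was sent to them.
- *The blinded-review wording in 19.1.4 is equally false.* A committee can review masked summaries in an open-label trial. The wording lacks a mechanism, but it is a different claim.

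Central MRI reading, expert review of relapses and the rule that missing causality counts as related are real safeguards. None of them covers a site's recorded severity grade, causality assignment or EDSS score.

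**Conclusion.** The point holds. Protocol 10.2.2 attributes to the trial a property that its design does not have and that SAP 2.7 denies for participants. For patients the contradiction is direct. For investigators it rests on the open-label design, the printed map from order to dose and the absence of any masking procedure in the visible text. That last element assumes that no such procedure sits in redacted text or in a separate manual.

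There is no numerical size: no sample size, error rate or planned estimate changes. The effect is on interpretation. Adverse-event causality and severity, and through them the events of special interest and two of four DSMB triggers, together with EDSS and investigator-reported relapse, cannot be described as free of assessment bias on grounds of blinding. The documents give no estimate of how much bias, if any, arose. The correction is worth making because it is cheap and governs what the report may conclude.

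**What to change.** 1. Protocol 10.2.2: remove the claim of dose blinding and of an unbiased evaluation. Keep the equal-cell-count and anaemia or iron-deficiency rationale. If no further protocol version is planned, record the correction in the SAP, or an addendum to it, and in the study report.
2. SAP 2.7 and the clinical study report: state that adverse-event causality and severity, EDSS and relapse reporting were not blinded to dose, and name investigators as well as patients.
3. Protocol 19.1.4: reconcile rather than delete. State whether the Steering Committee's safety review is masked to dose group and, if so, how.
4. State whether the central MRI readers and the relapse-confirming neurologist were masked to dose group. Withhold dose group from them for any outstanding or repeat reads. SAP Final 2.0 followed data review and already has rules for merging vendor MRI data, so this may not reach reads already completed; for those, disclosure is the remedy.

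The cost is wording, plus withholding one item from any remaining reads. The downside is a weaker claim about freedom from assessment bias.

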### 10.2.3 Method of Administration

Study treatment will be administered on an outpatient basis. The product bag(s) should be taken out from the fridge or cooling box approx. 30 min prior to the application. A bedside test for blood group or cross-matching procedures will be performed according to local regulations and prior to infusion. The administration of CLS12311/placebo is performed by i.v. infusion of the entire product bags over a 30 to 60-minute period using a standard blood component kit with inline filter (40 µm). The infusion should typically run with 5 ml/min, corresponding to approx. 1.7 drops per second. Standard study site guidelines will be followed to ensure sterility of the material and appropriate methods for intravenous administration.

The Investigator or his representative will document the time and volume of CLS12311/placebo administration for each patient. For incomplete volume administration (e.g. discontinuation due to AE), the reasons must be documented.

CLS12311 (or placebo) infusions should be initiated and supervised by an experienced professional with access to appropriate medical support to manage severe reactions (see Appendix 24.2).

All patients will be observed at the clinical site for at least 2 hours after the completion of the administration of the CLS12311/placebo. After completion of the infusion, the i.v. cannula should remain in situ for at least 2 hours to allow for administration of drugs intravenously, if necessary, in the event of a delayed reaction. If no adverse event occurs during this period of time, the i.v. cannula may be removed, and the patient may be discharged\*.

AEs during administration and observation must be documented according to the procedures outlined in section 13.

*\* In Czech Republic, all patients will be admitted as inpatients and will be observed for 24 hours following administration of CLS12311.*

